9.2. Data Analyses

9.2.1. General Considerations

A detailed Statistical Analysis Plan (SAP) will be prepared and approved by the MAH prior to implementation. All SADRs, and ADRs of special interest will be recorded and coded using Medical Dictionary for Regulatory Activities (MedDRA) terms and presented by system organ class (SOC) and preferred term (PT). Anonymised characteristics of patients who are screened

for enrolment, but do not participate in the study, will be collected in screening logs and reviewed on an ongoing basis for the purposes of understanding enrolment trends.

9.2.2. Baseline Assessment

The demographic and clinical profile of the registry population will be described using baseline data. Continuous variables will be reported using appropriate measures of dispersion and central tendency and categorical variables will be summarized as number and percentage of the total registry population.

9.2.3. Primary Analyses

Cumulative incidence of SADRs, and ADRs of special interest will be calculated as the number of patients who have a specific event starting during the study period, divided by the number of patients enrolled, multiplied by 100.

Risk of SADRs, and ADRs of special interest will be estimated as number of events over cumulative time at risk. Time at risk will be defined as the time between dates of first dose of Esbriet to end of follow-up (completion of follow-up / registry withdrawal). Case narratives will be provided for each SADR.

Tables with counts of SADRs, and ADRs of special interest summarized by MedDRA SOC and PT, and stratified by fatal or non-fatal outcome will be provided. Analysis will be conducted, if possible, for subgroups of patients including: predisposing conditions for liver disease; concomitant immunosuppressive therapy and other therapy for IPF; advanced stages of IPF; secondary cause of pulmonary fibrosis; QT prolongation; underlying cardiac, hepatic and other forms of pulmonary disease; Esbriet use for conditions other than IPF; paediatric patients, and patients who have stable warfarin anticoagulation at the beginning of pirfenidone treatment.

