No formal hypotheses will be tested. The study population for analysis of safety will include any patient who receives at least one dose of Esbriet regardless of the length of follow-up for that patient. Descriptive analyses will include frequency and measures of central tendency, range, and dispersion of clinical characteristics of the study population. Frequencies and cumulative incidence of reported ADRs will be summarized.

Ethical Considerations:

The registry will be conducted in accordance with the ethical principles that have their origins in the Declaration of Helsinki,¹ applicable privacy laws, and local regulations for each participating site. This non-interventional study will be conducted in accordance with the Guidelines for Good Pharmacoepidemiology Practices (GPP)² issued by the International Society for Pharmacoepidemiology (ISPE). When applicable, an independent ethics committee (IEC) will review and approve the protocol before any patient is enrolled. Appropriate informed consent and paediatric assent will be obtained from participating patients or their parents or legal representatives, if applicable.

Table 1: Registry Schedule of Assessments

Data Collected	Baseline	Follow-up visits (every 3 months ± 4 weeks)
Visit ID	1	2-9
Informed consent	X	-
Patient/legal representative and secondary contact information	X	X
Primary health care provider information	X	X
Demographics [age, gender, race/ethnicity (where allowed by local regulation), smoking history, alcohol use]	X	-
Medical history	X	-
Concurrent diseases	X	-
IPF history (date of diagnosis/duration of disease, method of diagnosis, pulmonary function at initiation of Esbriet®, oxygen supplementation)	X	-
Prior and concomitant treatments for IPF	X	X
Reason for Esbriet therapy (other than IPF)	X	-
Prescribed Esbriet treatment (initial dose, dose changes/discontinuation, reason for change/discontinuation)	X	X
Other (concomitant medications, height, weight, liver function tests)	X	-
Warfarin treatment	X	X
Esbriet discontinuation	information about and date of last Esbriet dose	
SADRs ^a	assessed throughout study	
ADRs of special interest ^a	assessed throughout study	
Relevant laboratory and clinical tests, Esbriet dose, and concomitant medications corresponding to reported ADRs	collected when associated with SADR or ADR of special interest	
Patient withdrawal from the registry ^b	collected as patient completes study or withdraws before completing study	

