3. OBJECTIVE

The objective of this study is to evaluate the long-term safety profile of Esbriet in patients with IPF and to monitor for any unknown or potential risks of treatment with Esbriet.

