4.2. Setting

The registry aims to initially enrol patients from approximately 100 pulmonary clinics throughout selected EU Member States and is open to all patients who will receive Esbriet. Enrolment will stop when 1,000 patients with a diagnosis of IPF have been enrolled. It is estimated that the enrolment will be completed within approximately 24 months. The MAH will closely monitor enrolment and will keep the Rapporteur and Co-Rapporteur informed of progress with the registry at regular intervals. If progress is not satisfactory, then the MAH will discuss with the Rapporteur and Co-Rapporteur any contingency that might be considered in order to increase the recruitment level in the context of the overall usage of the product within the EU. These may include, but are not limited to, extending the registry into another Member State, opening up more sites and intensifying the communication plan.

Each patient will be followed for up to 2 years. The MAH will also closely monitor the retention of patients and will undertake all reasonable efforts and methods to minimize loss to follow-up for the entire duration of the registry. Treating physicians will collect pre-specified data at the baseline and every 3 months thereafter, for the duration of the patients' participation in study.

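### The primary cumulative incidence is a crude proportion that takes no account of shortened observation, and the companion pooled rate cannot separate early from late risk

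*Protocol*

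**What the plan says.** Protocol Section 9.2.3, Primary Analyses, fixes two measures for SADRs and ADRs of special interest.

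- **Cumulative incidence** is "the number of patients who have a specific event starting during the study period, divided by the number of patients enrolled, multiplied by 100". No time point, censoring rule or use of event dates is given.
- **Risk** "will be estimated as number of events over cumulative time at risk". Time at risk is "the time between dates of first dose of Esbriet to end of follow-up (completion of follow-up / registry withdrawal").

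Observation is unequal by design. Section 4.2 states: "Each patient will be followed for up to 2 years". Section 5.7 lets patients withdraw at any time. The Synopsis (Statistical Considerations) counts "any patient who receives at least one dose of Esbriet regardless of the length of follow-up for that patient", and Section 7 likewise takes treated patients as the safety population.

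The protocol does not state one window for collecting ADRs:

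- The Synopsis (Registry Settings) and Section 7.2 end collection 28 days after the last dose in patients who stop Esbriet. Section 7.2 also opens by saying that collection runs to the end of the 2-year follow-up.
- Section 5.7 ends it at the earlier of that date and registry withdrawal.
- Section 7.3 uses the later of registry discontinuation and 28 days after the last dose.

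The objective in Section 3 is to "evaluate the long-term safety profile of Esbriet in patients with IPF". Section 9.3 rules out imputation and leaves further details on missing data to the SAP.

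**The concern.** Under the stated formula every enrolled patient stays in the denominator for the whole study. A patient lost at month 2, or whose ADR collection ended early because Esbriet was stopped, counts the same as one observed event-free for 2 years. The reported percentage therefore falls as retention worsens, which is the reassuring direction for a safety study.

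The second measure uses person-time and so does allow for unequal follow-up. It raises three other problems. One average over all follow-up mixes early tolerability with later exposure, whereas the objective is the long-term profile. It is called a risk although it is events per unit of time. Its denominator runs to completion or registry withdrawal, so it may include time in which, under Section 7.2, ADRs are no longer collected.

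**Working it through.** **The plan's own figure.** Section 9.1, Table 2, gives the 95% half-width for n = 1000. At 10%: 1.96 × √(0.10 × 0.90 / 1000) = 1.86%, as stated. All eight rows reproduce. The calculation treats all 1000 patients as complete binomial observations.

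**Crude proportion when observation is cut short.** The protocol gives no attrition figure, so the share d whose observation ends by 2 years is an assumption and is varied. Take a true 2-year risk of 10%, a constant hazard and exponential censoring:

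- h = −ln(0.90)/2 = 0.0527 per year; c = −ln(1 − d)/2
- crude = h/(h + c) × [1 − exp(−2(h + c))]

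| d (all censoring) | c per year | Crude | Bias (points) |
|---|---|---|---|
| 10% | 0.0527 | 9.5% | −0.5 |
| 20% | 0.1116 | 9.0% | −1.0 |
| 40% | 0.2554 | 7.9% | −2.1 |
| 60% | 0.4581 | 6.6% | −3.4 |

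The ratio of crude to true risk is nearly the same for true risks from 2.5% to 22%, the range of ADR incidences in Section 9.1: about 0.95 at d = 10% and 0.66 at d = 60%.

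**When part of the attrition is a competing event.** Keep 40% leaving observation in total (c = 0.2554), but let only part of it be loss, with hazard g = −ln(1 − loss)/2, and the rest a competing event with hazard k = c − g. The target is then h/(h + k) × [1 − exp(−2(h + k))]. The crude value stays at 7.87%.

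| Loss | k per year | Target | Bias (points) |
|---|---|---|---|
| 5% | 0.2298 | 8.05% | −0.18 |
| 10% | 0.2027 | 8.25% | −0.38 |
| 20% | 0.1438 | 8.71% | −0.85 |

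If observation ends only by death, the crude proportion equals the competing-risk cumulative incidence and the bias is zero.

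**Pooled rate and timing.** Assume 40% censored and a hazard of 0.40 per person-year in months 0 to 3, then 0.08. Mean person-time per patient is 0.242 years in the first interval and 1.324 years afterwards. The pooled rate is (0.40 × 0.242 + 0.08 × 1.324)/1.566 = 0.129 per person-year, 62% above the later rate. A hazard rising from 0.08 in year 1 to about 0.19 in year 2 gives the same figure: (0.08 × 0.883 + 0.193 × 0.684)/1.566 = 0.129. One reported number fits opposite long-term patterns.

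Converting the pooled first-event rate to a 2-year risk can err in either direction. The columns show d = 20, 40 and 60%:

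| Hazard per year | True 2-year risk | Implied by rate | Crude |
|---|---|---|---|
| 0.20 for 6 months, then 0.02 | 12.2% | 13.3, 14.2, 15.5% | 11.6, 10.9, 10.1% |
| 0.02 in year 1, 0.10 in year 2 | 11.3% | 10.7, 10.2, 9.5% | 9.8, 8.1, 6.3% |

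Under a constant hazard, with person-time that ends when observation ends, the rate is unbiased.

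**Time at risk against collection.** Suppose collection stops 28 days (w = 28/365.25 = 0.077 years) after the last dose, while patients who stop stay registered to 2 years and contribute time until then. With c now the hazard of stopping, the reported rate divided by the true rate is [w + (1 − exp(−c(2 − w)))/c]/2. This gives 0.95, 0.90, 0.80 and 0.68 for 10, 20, 40 and 60% stopping. Under the later-of rule in Section 7.3 this dilution would not arise.

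**The case against.** The strongest reply is that the two measures belong together. The rate in the same section handles unequal follow-up, the study is descriptive and tests no hypotheses, SADR narratives are provided, and the SAP promised in Section 9.2.1 may add time-to-event displays. Sections 4.2 and 6.4 also commit to retention and tracing, so loss may be small. Much of this stands. A reader should not infer that both measures ignore follow-up or that both understate risk: the person-time rate allows for follow-up and can err either way.

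A reader might also point to the stated median survival of 2 to 5 years as a source of bias in the crude figure. It is not one, because death is a competing event and patients who die belong in the denominator of a real-world probability. That survival is also counted from diagnosis, not from first dose.

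Nor does the protocol support saying that the crude figure cannot be compared with the 75-week incidences in Section 9.1, since it does not say how those were calculated.

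The appeal to the SAP does not settle the matter. The formula for cumulative incidence is written out in the protocol under Primary Analyses, so a SAP that replaced it would depart from the protocol. It is a stated rule, not a detail left open.

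**Conclusion.** The point holds for the crude proportion. As defined, it understates 2-year risk to the extent that withdrawal, loss or end of collection after stopping cuts observation short. Its size depends on an attrition mix that the protocol does not give: from 0.5 to 3.4 points on a true 10% if 10 to 60% are censored, but only about 0.2 to 0.8 points if 40% leave and 5 to 20% are lost. It is tempting to conclude that the bias exceeds the 1.86-point precision in Table 2. That is so at 40% attrition only if all of it is censoring (−2.1 points). In the mixed cases the bias is smaller than the half-width. All these figures assume a constant hazard and exponential, non-informative censoring.

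The pooled rate is a valid summary of average incidence if its person-time matches the collection window. It is mislabelled, it cannot separate early from late hazard, and its denominator conflicts with the collection rule in Section 7.2. It would go too far to say that the registry cannot show long-term safety: 2-year prospective data are collected, and the limit lies in these two summaries. The point should be addressed but does not undermine the study.

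**What to change.** Amend Section 9.2.3 as follows and carry the changes into the SAP.

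1. For each SADR and ADR of special interest, add an Aalen-Johansen cumulative incidence from first dose at 3, 6, 12 and 24 months with 95% confidence intervals. Treat death as a competing event, and withdrawal, loss and end of ADR collection as censoring. Add a sensitivity analysis with discontinuation of Esbriet as a competing event, because stopping may be related to the risk of an ADR.
2. Split events and person-time by interval since first dose (for example 0–3, >3–6, >6–12 and >12–24 months) and call the result an incidence rate.
3. Keep the crude percentage as description, with treated patients as the denominator to match the Synopsis and Section 7. Section 5.5 allows enrolment before the first dose, so enrolled and treated patients may differ.
4. Reconcile the ADR collection window and the time at risk across Sections 5.7, 7.2, 7.3 and 9.2.3, so that person-time counts only while events are collected.

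The cost is slightly wider intervals, some programming and a wording amendment. First dose, last dose and withdrawal already feature in the planned data or definitions. The date of death must be captured. If that is a new data item, Section 11.4 may require renewed consent.

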9. DATA ANALYSIS AND STATISTICAL CONSIDERATIONS

9.1. Sample Size

The registry aims to enrol 1,000 patients with IPF across participating EU Member States. The sample size was selected in order to have sufficient statistical precision as expressed by a 2-sided, 95% confidence limit around the expected incidence rate for each ADR.

The incidence of ADRs during the 75 weeks of exposure among 789 unique patients treated with Esbriet in Phase 3 studies and 2 open-label studies ranged from 2.5% to 22%.

Table 2 shows the precision with a sample size of 1000 for varying rates of ADRs. Precision is defined as half the width of the 95% confidence interval. For example, if the expected proportion of abnormal LFT is 2.5% for a sample size of 1,000, the precision is 0.97%. The precision shown in the table was calculated based on 95% normal approximation confidence interval. The calculation of the confidence intervals was performed using PASS software⁶.

Table 2: Precision for Estimates of ADRs of Varying Proportions with Sample Size of 1000

Expected proportion	Precision
0.5%	0.44%
2.5%	0.97%
5.0%	1.35%
7.5%	1.63%
10.0%	1.86%
15.0%	2.21%
20.0%	2.48%
25.0%	2.68%

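### Section 9.2.3 gives the name 'Risk' to a total-event rate, and no planned measure is both patient-based and adjusted for unequal follow-up

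*Protocol*

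**What the plan says.** Section 9.2.3 of the protocol (Primary Analyses) defines two measures, one after the other.

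- The first counts patients: "Cumulative incidence of SADRs, and ADRs of special interest will be calculated as the number of patients who have a specific event starting during the" (the sentence goes on to name the period of the study). The divisor is everyone enrolled, and the result is a percentage.
- The second counts events: "Risk of SADRs, and ADRs of special interest will be estimated as number of events over cumulative time at risk". Its denominator is also defined: "Time at risk will be defined as the time between dates of first dose of Esbriet to end of follow-up (completion of follow-up / registry withdrawal").

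Section 9.2.3 has no first-event rule and does not say whether repeat events in one patient count. It plans no confidence interval for either measure. The synopsis says "No formal hypotheses will be tested" and describes descriptive summaries. It also includes every treated patient whatever the length of follow-up. Section 4.2 sets follow-up at up to 2 years per patient.

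**The concern.** The numerator changes from patients in the first measure to events in the second, and the clock runs on after a first event. Together these make a total-event rate the natural reading. That is a valid description of burden, but it is not a risk. It can exceed the rate at which patients become affected by any multiple, depending on how often reactions recur. Several reactions of special interest in Section 7.2 can recur in one patient: gastrointestinal symptoms, dizziness, rash, fatigue and falls.

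The neighbouring cumulative incidence does not fill the gap. It is immune to repeats, but it divides by everyone enrolled, however long they were followed. Follow-up will vary: it is capped at 2 years, any length is accepted, and Section 2 gives a median survival after diagnosis of 2 to 5 years. The person-time measure is the only planned one that adjusts for this, and it does so per event. A reader who wants the rate at which patients first experience a reaction, allowing for time observed, will not find it. A reader who takes the label at face value will use the event rate in its place.

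**Working it through.** **The plan's own figures.** The only interval figures are in Table 2 of Section 9.1, where half-width = 1.96 × √(p(1−p)/1000). For p = 2.5% this gives 0.968% (stated 0.97%), and for p = 10% it gives 1.859% (stated 1.86%). All eight rows reproduce. They are binomial on patients, so repeat events do not affect them.

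**Inputs for the illustration.**
- 1,000 patients (Section 9.1).
- 2 years each, so 2,000 person-years. This is the maximum under Section 4.2 and is assumed here.
- Share affected: 2.5%, 10% or 22%. The outer values are the range quoted in Section 9.1 for 75 weeks of exposure and are used only as plausible levels.
- Mean episodes per affected patient, m: 1, 1.5, 2 or 3. The protocol gives no figure, so this is an assumption.
- First events occur on average at 1 year (assumption), so each affected patient gives up 1 year when time is cut at the first event.

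**Formulas.** Event rate as written = affected × m / 2,000. First-event rate = affected / (2,000 − affected × 1).

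Rates per 100 person-years:

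| Patients affected | As written, m = 1 | m = 1.5 | m = 2 | m = 3 | First-event rate |
|---|---|---|---|---|---|
| 25 (2.5%) | 1.25 | 1.88 | 2.50 | 3.75 | 25/1,975 = 1.27 |
| 100 (10%) | 5.0 | 7.5 | 10.0 | 15.0 | 100/1,900 = 5.3 |
| 220 (22%) | 11.0 | 16.5 | 22.0 | 33.0 | 220/1,780 = 12.4 |

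At m = 3 the written measure is 2.7 to 3.0 times the first-event rate. At m = 1 it is slightly lower, because time after the event stays in the denominator.

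**Why cumulative incidence is no substitute.** Take a constant first-event rate of 0.0526 per year (100/1,900). The expected share affected is 1 − exp(−0.0526) = 5.1% with 1 year of follow-up, and 1 − exp(−0.1053) = 10.0% with 2 years. The same underlying rate gives about half the cumulative incidence when follow-up is halved.

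**If an interval were put on the event rate.** Take 10% affected and exactly 3 episodes each. The total is 300 events, with variance 1,000 × (0.1 × 9 − 0.3²) = 810. The standard error relative to Poisson is √(810/300) = 1.64. With geometric counts of mean 3, E[k²] = 15, the variance is 1,000 × (0.1 × 15 − 0.3²) = 1,410, and the ratio is 2.17. With one event each, the variance is 1,000 × (0.1 − 0.01) = 90 on 100 events, and the ratio is 0.95. A Poisson interval would therefore be too narrow only if reactions recur.

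**The end of the clock.** Four sections bear on when a patient stops being at risk of a recorded reaction:
- Section 5.7: 28 days after the last dose or registry withdrawal, whichever is first.
- Section 7.2: opens with collection to the end of the 2-year follow-up, then ends it 28 days after the last dose for patients who stop treatment.
- Section 7.3: registry discontinuation or 28 days after the last dose, whichever is later.
- Section 9.2.3: the denominator runs to completion or withdrawal.

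A first-event rate needs one end date, so these must be reconciled.

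**The case against.** Events over person-time is a legitimate safety measure. It describes total burden, and if repeats count, letting time run on is the right denominator. The patient-level question has a planned answer in the cumulative incidence. Case narratives for each serious reaction would show repeats among the serious ones. That repeats count is inferred, since no sentence says so. Collection is limited to clinically significant reactions considered at least possibly related, which restrains the number of trivial repeats. Detail is also left to an analysis plan that is not shown.

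Most of this stands, and it limits the point to the label and the missing measure. It does not remove the point, because the protocol itself fixes the formula and the name, and cumulative incidence ignores time.

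A reader might infer three stronger things that the documents do not support:
- *Planned intervals are too narrow.* The protocol plans no interval for this rate, so the 1.64 and 2.17 above describe a hypothetical analysis.
- *The sample-size precision is affected.* Section 9.1 speaks of a "95% confidence limit around the expected incidence rate for each ADR", but Table 2 concerns proportions of patients and is untouched by repeats.
- *A few patients drive the figure.* That could happen, but there are no recurrence data to show it, and in the illustration above with three episodes each no minority dominates.

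**Conclusion.** The point holds as one of definition and labelling with a practical consequence. The measure called 'Risk' in Section 9.2.3 is, on its natural reading, a total-event rate, and it cannot be read as a patient's risk for reactions that recur. No planned measure is both patient-based and adjusted for follow-up. The size depends wholly on recurrence, which is assumed: 15 against about 5.3 per 100 person-years at three episodes each with 10% affected, and no material gap at one episode each. These figures also assume a full 2 years for everyone and first events at 1 year on average. The change is worth making before analysis because it alters a reported primary result.

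**What to change.** In Section 9.2.3:

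1. Define the risk measure as the number of patients with a first event of the given type, divided by the sum of time from first dose to that event or to the end of the reaction collection window, whichever comes first. Reconcile the end of that window across Sections 5.7, 7.2, 7.3 and 9.2.3 and use one definition.
2. Keep total events over person-time as a companion measure, call it an event rate, and state that repeat events count.
3. If an interval is reported for the event rate, use a patient-clustered or overdispersed variance.

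The cost is wording and one extra table. First-dose dates are already needed for the planned time at risk, and event start timing for the planned cumulative incidence, so no new data are required. The headline figure will be lower for recurrent reactions. If the reconciled window closes before registry follow-up ends, the denominator shrinks and the rate rises. The protocol gives no discontinuation figures from which to size that.

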with a diagnosis of IPF have been enrolled. It is estimated that the enrolment will be completed within approximately 24 months. The Marketing Authorisation Holder (MAH) will closely monitor enrolment and will keep the Rapporteur and Co-Rapporteur informed of progress with the registry at regular intervals. If progress is not satisfactory, then the MAH will discuss with the Rapporteur and Co-Rapporteur any contingency that might be considered in order to increase the recruitment level in the context of the overall usage of the product within the EU. These may include, but are not limited to, extending the registry into another Member State, opening up more sites and intensifying the communication plan.

Each patient will be followed for up to 2 years. The MAH will also closely monitor the retention of patients and will undertake all reasonable efforts and methods to minimize loss to follow-up for the entire 2 years of observation.

Treating physicians will collect pre-specified data at baseline and approximately every 3 months thereafter for the duration of the study. In the event that a patient discontinues Esbriet treatment, all serious adverse drug reactions (SADRs), and adverse drug reactions (ADRs) of special interest will be collected until 28 days after the last dose of Esbriet.

Treatment:

The registry is observational; therefore, all treatment decisions are at the discretion of the patient's health care provider and are not mandated by study design or protocol. Cooperation of health care professionals is based on goodwill and no contractual sanctions will be applied by the MAH.

Inclusion Criteria:

- A clinical decision has been made, prior to study enrolment, to prescribe Esbriet
- Patients who are newly prescribed Esbriet therapy
- Initiation of Esbriet therapy is not more than 30 days prior to study enrolment
- Patient or legal representative provides informed consent and/or informed assent according to local regulations

Esbriet is only indicated for the treatment of mild to moderate idiopathic pulmonary fibrosis in adults. The registry protocol does not encourage use of Esbriet for other conditions or in paediatric patients. However, if a physician, in collaboration with the patient and/or legal representative, makes an independent clinical decision to prescribe Esbriet outside the terms of the Summary of Product Characteristics (SPC), those patients may be included in the registry.

Exclusion Criteria:

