5.7. Patient Withdrawal

Patients may withdraw consent and discontinue registry participation at any time, without prejudice. Physicians will complete a registry withdrawal case report form (CRF) and all reasonable efforts will be made to establish whether the reason for withdrawal was related to an ADR. Information collected during study participation will be retained for analysis unless the

patient specifically requests otherwise. In the event that a patient discontinues Esbriet treatment prior to registry withdrawal, all SADRs and ADRs of special interest will be collected until 28 days after the last dose of Esbriet or until registry withdrawal, whichever comes first.

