7.2. Safety Data Collection

The following will be collected from the point of the first dose with Esbriet and will continue through the end of the follow-up period (2 years):

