1. SADR
2. Clinically significant ADRs of special interest: These ADRs of special interest encompass all "important identified risks" and "important potential risks" as defined in the Esbriet Risk Management Plan and include:
 - Photosensitivity reactions and skin rashes
 - Abnormal liver function tests
 - Dizziness
 - Weight loss

- Gastrointestinal symptoms
 - Fatigue
 - Falls
 - Drug interactions (including smoking)
 - Increased platelet counts
 - Specific cardiac events: supraventricular tachyarrhythmia, atrioventricular block/sick sinus syndrome, ventricular arrhythmia, bundle branch block, aortic or pulmonic valvular incompetence
 - Blood dyscrasias: agranulocytosis, leukopenia, neutropenia
 - Angioedema
 - Any other clinically significant ADRs based on the judgment of the prescriber
3. Information to be collected in association with reported ADRs (including, but not limited to):
- a. Prescribed Esbriet dose changes and reasons for change
 - b. Concomitant medications including treatments for IPF (those stopped or started within 28 days prior to the event). The following minimum data elements will be collected:
 - Medication name
 - Dose and duration of exposure
 - Indication for use
 - c. Relevant laboratory and clinical tests

In the event that a patient discontinues Esbriet treatment, all SADRs, and ADRs of special interest will be collected until 28 days after the last dose of Esbriet. All serious and reportable ADRs will be followed until resolution or until the end of the follow-up period, whichever comes first.

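### The person-time rate in section 9.2.3 runs to registry exit, while the protocol gives conflicting windows for collecting ADRs; under the 28-day rule the rate is biased low

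*Protocol*

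**What the plan says.** Section 9.2.3 gives two measures for SADRs and ADRs of special interest. The first is cumulative incidence: patients with the event over patients enrolled. The second is a person-time rate, which "will be estimated as number of events over cumulative time at risk". For that rate, "Time at risk will be defined as the time between dates of first dose of Esbriet to end of follow-up", and the end of follow-up is glossed as completion of follow-up or registry withdrawal. Stopping Esbriet is not an end point.

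The protocol sets the period for collecting events in several places, and they differ:

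- Synopsis, for patients who stop Esbriet: "adverse drug reactions (ADRs) of special interest will be collected until 28 days after the last dose of Esbriet".
- Section 7.2, closing text, same situation: "all SADRs, and ADRs of special interest will be collected until 28 days after the last dose of Esbriet".
- Section 5.7, for patients who stop Esbriet before leaving the registry: "until 28 days after the last dose of Esbriet or until registry withdrawal, whichever comes first".
- Section 7.2, opening text: collection runs from the first dose to the end of the 2-year follow-up.
- Section 7.3: ADRs are reportable up to the later of registry discontinuation and 28 days after the last dose.

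**The concern.** A rate is sound only if its numerator and denominator cover the same time. If collection closes 28 days after the last dose, a patient who stops Esbriet and stays registered goes on adding person-time in which, by rule, no event can be counted.

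The protocol expects such patients. Section 5.7 treats stopping the drug and leaving the registry as separate events, Table 1 and section 8.1 list them separately, and the synopsis commits the MAH to limiting loss over the full 2 years. The better that retention works, the larger the surplus denominator.

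The error has one direction: the rate comes out too low and the drug looks safer. It can also distort the subgroup analyses planned in 9.2.3, because subgroups that stop the drug at different rates would be diluted to different degrees.

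**Working it through.** **The plan's own figure.** Table 2 is the only computed result in the protocol. With 1.96 × √(p(1−p)/1000), all eight rows reproduce to two decimals (for example, p = 2.5% gives 0.968%, stated as 0.97%). The table concerns proportions, so it neither supports nor contradicts the person-time rate.

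**Windows side by side.**

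| Source | Collection ends | Matches the 9.2.3 denominator? |
|---|---|---|
| Synopsis; 7.2 closing text | last dose + 28 days | No, if the patient stays registered longer |
| 5.7 | earlier of last dose + 28 days and withdrawal | No, same condition |
| 7.2 opening text | end of 2 years | Yes |
| 7.3 | later of registry discontinuation and last dose + 28 days | Yes, but off-drug time is included |

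**One patient under the 28-day rule.** Take 2 years as 730.5 days and a month as 30.4375 days. A patient who stops at month 6 and stays to year 2 is observable for 182.6 + 28 ≈ 211 days, 29% of the time counted. The other 520 days can hold no countable event. Stopping at month 12 leaves 337 such days, and at month 18 leaves 155.

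**Whole registry under the 28-day rule.** The protocol gives neither the proportion D stopping Esbriet by 2 years nor the share q of stoppers who stay to 2 years, so both are assumed. Time to stopping is taken as exponential, and stoppers who do not stay leave at last dose + 28 days. The events counted are the same whichever denominator is used, so:

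reported rate / observable-window rate = mean observable time / mean time in registry.

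With F = 2 years, g = 28/365.25 = 0.077 years and λ = −ln(1−D)/2, the mean observable time is

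m = g + [1 − exp(−λ(F−g))]/λ.

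For D = 30%: λ = 0.17834, exp(−0.17834 × 1.9233) = 0.70963, and m = 0.0767 + 0.29037/0.17834 = 1.705 years. Mean time in registry is 2 if all stoppers stay and 1 + m/2 if half stay.

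| D | m (years) | Ratio, all stay (m/2) | Understatement | Correction factor | Ratio, half stay | Understatement |
|---|---|---|---|---|---|---|
| 20% | 1.808 | 0.904 | 10% | ×1.11 | 0.95 | 5% |
| 30% | 1.705 | 0.852 | 15% | ×1.17 | 0.92 | 8% |
| 40% | 1.596 | 0.798 | 20% | ×1.25 | 0.89 | 11% |
| 50% | 1.481 | 0.740 | 26% | ×1.35 | 0.85 | 15% |

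If no stopper stays, the ratio is 1. Early stopping makes it worse: if 30% stop at month 3 and all stay, m = 0.3 × (0.25 + 0.077) + 0.7 × 2 = 1.498 years and the ratio is 0.749, an understatement of 25% against 15% with exponential stopping.

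**Subgroups.** If 50% stop in one subgroup and 20% in another, and all stay, two equal true rates would show a ratio of 0.740/0.904 = 0.82. The subgroup that stops more often would look safer.

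**The case against.** The strongest objection is that the 28-day stop is not the protocol's only rule. Section 7.3 keeps reporting open to registry discontinuation, and the opening of section 7.2 runs to 2 years. If either governs, the later time is observed and there is no dead time. This stands. A reader who sees only the 28-day sentences might infer that every rate in the registry is diluted; the documents do not support that. The opening of 7.2 can be read as the general rule, with the section's closing text as the exception for patients who stop. Section 7.3 cannot be reconciled in that way. Nor does it fully rescue 9.2.3: section 7.1 limits ADRs to events at least possibly related to Esbriet, so months off the drug can be expected to yield few of them, and the rate would pool on-drug with mostly off-drug time.

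A reader might also take this rate for the registry's main safety measure, and conclude that the flaw hides signals. That does not follow. Cumulative incidence comes first in 9.2.3, is the measure named in the synopsis and matches the proportions used for Table 2. It does not use person-time, and neither do the SOC and PT counts or the SADR narratives. A reaction that makes a patient stop early is still counted in the numerator.

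The protocol does not say what completion of follow-up means for a patient who has stopped Esbriet. If it meant the 28-day point, the bias would vanish. Section 9.2.3 does not say so.

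Finally, a reader might count it as an error that death and loss to follow-up are not named as ends of time at risk. Such censoring rules can be left to the SAP, so this is not part of the point.

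**Conclusion.** The point holds in a conditional form. The protocol fixes a denominator that runs to registry exit and, in three places, a collection window that can close well before it. Under those places the person-time rate is biased downward as soon as some patients stop Esbriet and remain registered for more than 28 days. Under section 7.3 there is no unobservable time, but the rate blends on-drug and off-drug experience. Sites following different sections would also collect events over different periods.

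The direction under the 28-day rule is certain; the size is not, because the documents give neither the stopping rate nor the retention of stoppers. For 20% to 50% stopping by 2 years, the 10% to 26% range is the case in which every stopper stays the full 2 years. With half staying the bias is roughly half to 60% as large, and with none staying it is nil. Cumulative incidence is not affected in this way.

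**What to change.** First reconcile the collection windows in the synopsis, section 5.7, both parts of section 7.2 and section 7.3, so that one rule applies at every site.

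Then amend section 9.2.3 so that numerator and denominator use the same window. Report an on-treatment rate whose time at risk ends at the earlier of last dose plus 28 days and registry exit, counting only events with onset in that window. If the reconciled rule also collects later events, report them as a separate off-treatment rate over its own person-time, so that valid long-term observations are kept and not blended in.

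The cost is small: wording in the sections named, a short change in 9.2.3, and a little more derivation work. Table 1 already collects the date of the last dose, so no new data are needed. Reported on-treatment rates will be somewhat higher, that is, less favourable, to the extent that stoppers stay in the registry.
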